9.4 Data Monitoring

To achieve robust and unbiased results, data will undergo a rigorous quality control process to ensure consistency in scoring, coding and accuracy of data entry. Additionally, 20% of all data folders will undergo a random audit every replicate. Also see **Data Management** procedures and **Quality Assurance** detailed below.

9.5 Interim Data Analyses

Interim analyses will be conducted in June of 2019, after the pilot, first, and second replicates are completed. We expect that 140 participants will have completed post-test at this time. The purpose will be to confirm feasibility of the training conditions, to assess effect size on cognitive measures from pre- to post- training and adapt number of sessions, if warranted, and to monitor safety.

Interim analyses will be conducted to ensure the safety of the trial. Per NIA, this project does not meet the criteria for requiring a formal Data and Safety Monitoring Plan or Data Safety Monitoring Board because it is not a Phase III clinical trial as defined by NIH. As a behavioral intervention study, this is a phase II efficacy trial¹. At interim analysis, [name] will compare the number of adverse events between the two randomized conditions to assess safety. The two groups will also be compared on attrition rates. Any significant differences between the two conditions in adverse events or attrition rates will be further investigated by [name]. If there is a significant imbalance, confirmed, then [name] will report the findings to the Clinical Trial Coordinator, [name], who is unblinded. The Clinical Trial Coordinator will work with the IRB to decide if the study should be terminated early.

Interim analyses will be conducted to ensure the feasibility of study intervention adherence. If at interim analyses, less than 75% of participants randomized to an arm complete at least 16 sessions (80% of prescribed 20), the intervention arm will be deemed not feasible. If this occurred for both arms, the study will end.

Finally, interim analyses will examine the potential efficacy of the piano training arm. Effect sizes and confidence intervals for all cognitive outcomes will be calculated for pre- to post- training relative to controls. We expect that the piano training arm will produce an improvement of at least $d=0.25$ from baseline to post-test on at least one of the cognitive measures of verbal fluency (phonemic, category or switching), Trails A or B, or Digit Coding, relative to active controls. If an effect size from pre- to post- training relative to controls of this

magnitude is not observed on at least one of these outcomes, we will adapt study procedures by changing the number of training sessions from 20 to 25. In this instance number of training sessions completed will be examined as a covariate in final analyses.

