5.5 Describe the procedure for obtaining intervention group assignment

The study coordinator with the statistician will randomize participants stratified by MCI status. Participants with and without MCI will be randomized in a 1:1 ratio to either piano training or the active control condition of music listening instruction. To ensure balance throughout enrollment, randomization will be stratified by MCI status (present vs. absent) and conducted in varying blocks of participants as designed by Co-I Ji. [name] will generate the stratified permuted random blocks using R. [name] will maintain the random seed and the computer codes and will send the randomization list to the clinical trial coordinator. The treatment allocation will be denoted as A or B and recorded on the randomization form by the clinical trial coordinator. The study coordinator will control access to the randomization list and know whether A (B) stands for intervention (control). Study investigators [name], [name], and [name] will remain blind to participant condition. The testers will remain blind to participant condition. The trainers (including Co-I [name]) and clinical trial coordinator will be aware of participants' randomized condition.

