9.3 Sample Size

We expect up to 20% attrition after the initial in-person visit across the time period in which cognitive intervention study protocols will be administered. Our goal is to complete in-person screening visits for up to 450 participants in order to have up to 360 participants complete the study. We can tolerate higher rates of attrition. We require a minimum of 198 eligible participants with *at least* 99 individuals randomized to each condition (piano training, controls) to have adequate statistical power. With stratified randomization, this will result in *at least* 48 persons per MCI/no MCI subgroup.

Statistical power analysis using G*Power¹²³ in consideration of our pilot data effect sizes as well as attrition was conducted to estimate power. We will control type I error at .05 to achieve at least 80% statistical power.

To power **Specific Aim 1: To examine the efficacy of piano training to improve CAP, cognition, and everyday function among older adults**, a final n of 198 participants ($n=99$ per randomized condition) will achieve 95% power to detect a significant group x time interaction across baseline to immediate post-test, with an alpha of .05. This assumes a small effect size (f) of 0.10¹²⁴ (Cohen's f effect sizes are 0.10- small, 0.25- medium: f is roughly equivalent to $\frac{1}{2}$ of d when comparing two groups)¹²⁴.

To power **Specific Aim 2: To examine the moderating effects of MCI on intervention efficacy**, a final n of 168 will have .95 power at alpha .05 to detect medium effects ($f=.10$) for significant group x time x moderator three way interactions.

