11.1 Adverse Experience Reporting

Study staff will monitor participants and be alert to any adverse events at each study.. Testers and Trainers will ask participants about any adverse events at the end of each testing and intervention visit. Furthermore, the participants will be interviewed about any such events throughout their study participation at the post-test visit. Study staff will be alert to any volunteered adverse events. All such events will be documented on a standardized form. At all in-person contacts and at any other applicable time throughout the study, any potential adverse events reported by a subject or observed by the research staff will be recorded and subsequently evaluated by the Principal Investigator for its relation to the study research procedures and whether or not any corrective action need be taken. It is unlikely and not expected that any adverse incident will result from implementation of this study protocol. However, any and all adverse events that may occur will be recorded on the appropriate forms, and reported to the governing IRB, as applicable.

Any adverse events will be reported to the site IRB within 72 hours of occurrence or detection by PI [name]. In the unlikely event of a serious adverse event this report will be made within 24 hours and reported also to the NIH Project Officer. In the unlikely case of study-related serious adverse events, an interim analysis will be performed in order to determine whether a change in the risk/benefit ratio has occurred and reviewed by the statistician [name]. If so, this change will be brought to the attention of the USF IRB for review, current and future participants will be notified of this change, and stopping rules will be considered.

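### Section 9.5 lets its only scheduled by-arm comparison of adverse events and attrition go further only if it is significant; the test is undefined and, at about 70 per arm, has low power when events are uncommon

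*Combined protocol and SAP*

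**What the plan says.** Section 9.5 (Interim Data Analyses) sets the timing by the pilot and first two replicates: "We expect that 140 participants will have completed post-test at this time". Section 5.5 fixes the allocation: "Participants with and without MCI will be randomized in a 1:1 ratio". On safety, the person assigned to the analysis "will compare the number of adverse events between the two randomized conditions to assess safety", and attrition is compared as well. Two gates follow. The first is investigation: "Any significant differences between the two conditions in adverse events or attrition rates will be further investigated". The second is escalation, in a sentence that opens "If there is a significant imbalance, confirmed, then" and has the findings reported to the unblinded Clinical Trial Coordinator, who works with the IRB on whether to end the study early.

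Section 9.5 names no test, no significance level and no numerical margin for this comparison, and no power is stated. It records that the funder did not require a monitoring board. The analyses in 9.6 to 9.8 include no by-arm adverse-event comparison at the end of the trial. In 11.1, each event is recorded and "subsequently evaluated by the Principal Investigator for its relation to the study research procedures".

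**The concern.** A significance gate limits false alarms. It does little to guard against overlooking harm when the sample is small and events are uncommon, and at an interim safety look the second error is usually the more serious. As 9.5 is worded, a difference that falls short of significance triggers neither further investigation nor a report to the coordinator, however large the estimate or wide its interval.

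The gate is also stricter than the plan's other decision rules. In the same section, interim efficacy is judged from effect sizes and confidence intervals against d = 0.25, and feasibility from a plain 75% cut. In 9.6, baseline differences at p < .1 are enough to add a covariate.

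At stake is an excess of non-serious events in one arm, or a moderate difference in dropout. Either would show up mainly in a by-arm table.

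**Working it through.** **No figure to reproduce.** The documents state no power, detectable difference or event rate for this comparison.

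**Inputs**
- 140 post-test completers (9.5), 1:1 (5.5): 140/2 = 70 per arm.
- Attrition up to 20% (9.3): 140/0.8 = 175 randomized, about 87 per arm. Attrition has to be judged on this base, because completers have none.
- Alpha: 9.3 says "We will control type I error at .05 to achieve at least 80% statistical power". I assume that the .05 carries over to the safety comparison and is two-sided.
- Unit: participants with at least one event (assumed). Event counts are checked separately.
- Control event rate: not given, so a range is used.

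**Formula**

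power = Φ[(|p1 − p2| − 1.96·se0)/se1], with se0 = √(2·p̄(1 − p̄)/n) and se1 = √([p1(1 − p1) + p2(1 − p2)]/n).

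For 10% vs 20% with n = 70:
- p̄ = 0.15 and se0 = √(2 × 0.15 × 0.85/70) = 0.0604
- se1 = √((0.09 + 0.16)/70) = 0.0598
- (0.10 − 1.96 × 0.0604)/0.0598 = −0.31, and Φ(−0.31) = 0.38

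**Doubling at 70 per arm, exact binomial enumeration, two-sided .05**

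| Control vs other arm | Chi-square | Fisher |
|---|---|---|
| 2% vs 4% | 8.7% | 1.8% |
| 5% vs 10% | 20.4% | 11.4% |
| 10% vs 20% | 38.2% | 30.5% |
| 13% vs 26% | 50.1% | 42.1% |
| 15% vs 30% | 57.7% | 49.4% |
| 20% vs 40% | 74.7% | 68.3% |
| 25% vs 50% | 87.0% | 83.1% |

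The 50% crossing is at a control rate of about 13% by chi-square and about 15% by Fisher. A tripling from 5% to 15% is flagged 52% of the time (41% by Fisher).

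**Sensitivity**
- All randomized (87 per arm): 5% vs 10% gives 23% (Fisher 16%) and 10% vs 20% gives 45% (38%). The 50% crossing falls to about 11% (normal approximation).
- One-sided .05 at 70 per arm: 10% vs 20% rises from 38% to about 51%. The undefined alpha therefore matters.
- Event counts, exact conditional Poisson test: 7 vs 14 expected events, 26%; 14 vs 28, 53%; 28 vs 56, 85%.

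**Attrition at 87 per arm**
- 20% vs 30%: 34% (Fisher 27%).
- 20% vs 40%: 83% (Fisher 79%).

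**What the gate does to one data set.** Suppose that 7/70 and 14/70 participants have an event.
- The pooled rate is 21/140 = 0.15 and z = 0.10/0.0604 = 1.66, so p = .098 (Fisher .154).
- The risk difference is 10 points, with 95% CI 10 ± 1.96 × 5.98, or about −2 to 22 points.

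Under 9.5 this observed doubling requires no investigation and no report, although the interval reaches beyond a 20-point excess.

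**The case against.** The case on the other side is substantial, and it rules out several stronger readings that a reader might take from 9.5.

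- *The check would usually miss a doubling, whatever the event rate.* Not supported. Section 7 defines adverse events broadly, including soreness, eye strain or headache that increases in frequency and lasts over 24 hours, and participants are asked after every visit, of which there may be 23. High any-event rates are plausible, and above about 13% to 15% a doubling is usually detected. Section 9.5 also speaks of the number of events, and on counts power passes 50% at about 14 vs 28.
- *Attrition imbalance is equally exposed.* Only in part. A doubling from 20% to 40% is flagged about 83% of the time. Section 9.5 also has a per-arm rule with no p-value: an arm is deemed not feasible if fewer than 75% of those randomized to it complete 16 sessions. If true dropout is 30% and those participants also fall short of 16 sessions, the rule trips in 86% of trials at 87 per arm (82% at 70). Session completion is not the same as post-test attrition, so the cover is partial.
- *This is the only safety check, and imbalances never reach the IRB.* Not supported. Section 11.1 sends every adverse event to the IRB within 72 hours and serious ones within 24 hours, and a study-related serious event triggers an extra interim analysis with no significance condition. Section 11.3 adds unspecified safety analyses. What stands is that none of these is stated to compare arms.
- *Blinding makes an arm pattern invisible.* Not established. Section 5.5 says of certain named investigators and of the testers that they "will remain blind to participant condition", but trainers and the coordinator know the assignment, and trainers ask about events. The names are removed, so it cannot be confirmed that the Principal Investigator is among those blinded.
- *Non-significance is formally treated as no imbalance.* Section 9.5 does not say so. It only omits any further step.

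It is also fair that this is a phase II behavioral trial with low expected risk. That bears on how much weight the point deserves. It does not remove the gate.

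**Conclusion.** The point holds in a limited form. The one scheduled by-arm comparison of adverse events and attrition goes further only through a significance test that the plan does not define. On the assumptions of a two-sided .05 test, participants with an event as the unit, and 70 per arm, the chance of flagging a doubling is about 20% from a 5% control rate and 38% from 10% (11% and 30.5% by Fisher). It passes one half only above about 13% (about 15% by Fisher). For attrition the weakness lies in moderate differences such as 20% vs 30% (34%), not in a doubling from 20% (83%). The event rates are assumptions, so the size of the problem depends on how common events are in the control arm. This is a cheap improvement to monitoring. It does not show that safety oversight is absent.

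**What to change.** Amend 9.5 so that, at the interim, the statistician gives the unblinded coordinator, for the IRB, one table by arm with:

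- the number of adverse events and the number of participants with any event;
- dropouts among all randomized participants;
- risk differences with 95% confidence intervals for the participant-level rows, whatever the p-value.

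Remove significance as the condition for further review, and state the counting unit and denominator. The IRB's decision process stays as it is. The coordinator is already unblinded, so sending the table there unblinds no one further.

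The cost is one table and a sentence or two in 9.5, with no extra participants. The downside is that some chance differences will be looked at.

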9.6 Final Data Analyses

Dealing with Score Distribution. We will inspect the distribution of scores to confirm that parametric statistical testing is appropriate. In the event that distributional properties do not support parametric tests, we will compare the results from conventional parametric analyses with (a) results from similar nonparametric testing (e.g., Wilcoxon signed ranks test), (b) results from parametric analyses conducted after the non-normally distributed variables are transformed to improve normality to compare the results with the conventional parametric analyses, and (c) Any illegal values or outliers of $\geq \pm 3z$ will be checked for accuracy with the raw data.

Composite Outcomes. Data reduction in the form of principal component factor analysis (PCA) will be used to derive composite outcomes of CAP, cognition, and everyday function for analyses to reduce the number of comparisons. Baseline data across CAP, cognitive, and everyday function outcomes will be factor analyzed using pairwise deletions. Based on the number of factors derived and factor loadings of the individual measures (.4 or greater), outcome composite scores will be calculated after transforming the baseline data to z scores while taking into account the directional scaling of the items. Post-test scores will be standardized based upon the baseline mean and SD. The baseline factors and loadings will be applied to calculate post-test composite scores.

Preliminary/Descriptive Analyses. Prior to the analyses described below, we will conduct one-way ANOVA or Chi-square analyses as appropriate comparing the randomized groups at baseline on age, race, education, sex, MoCA, GDS, hearing and vision, to ensure that the study randomization procedures were successful. We will also confirm the equivalence of the two randomized conditions by comparing the NICT questionnaire responses. The total across the six items relevant to cognition will be calculated and examined in analyses. If even a marginally significant ($p < .1$) difference is observed for any of these study variables, the pertinent variables will be included as covariates in subsequent analyses.

Specific Aim 1: To examine the efficacy of piano training to improve CAP, cognition, and everyday function among older adults. We will compare changes in performance for piano training relative to control across the two measurement points (baseline, immediate post-test). We will use the PCA-derived composites of CAP and cognition, and everyday functioning as outcomes. We will use repeated measures analyses of variance within the mixed effects models, examining group as the between-subjects factor and time as the within-subjects factor. The group x time interaction will indicate whether the participants randomized to piano training change at differential rates over time relative to those randomized to the control group. This output will be obtained for each of the composite outcomes (CAP, cognition, and functional abilities). For aim 1 analyses and the composite outcomes of CAP, cognition, and everyday function, we will apply Holm-Bonferroni adjustments¹²⁵ to reduce Type I error. Specifically, the Holm-Bonferroni procedure uses a step-down process whereby p-values are sorted from lowest to highest, then the lowest p-value is used in its raw version, the second lowest p-value is multiplied by two, the third lowest p-value is multiplied by three and so on until the adjusted

p-value reaches or exceeds the pre-specified threshold for statistical significance, in our case a two-tailed p value of .05.

Intent-To-Treat Approach. We expect that some participants will not complete their intended followup according to the protocol for a variety of reasons, generating missing values. Intent-to-treat (ITT) analysis has become a widely accepted method for dealing with this issue. To maximize available information, we will employ statistical techniques that allow for the inclusion of missing data. Specifically, we will use linear mixed effects models to analyze data. This advanced analytical method allows for the inclusion of participants with missing data, so long as data are missing at random and offers flexibility with regard to the specification of the variance/covariance structure, which often leads to improved fit of the analytical model to the actual data. If there is non-ignorable missing data, we will apply pattern-mixture mixed effects models to assess the sensitivity of our findings with regard to missing data¹²⁶.

Specific Aim 2: To examine the moderating effects of MCI on intervention efficacy. We will also test for moderation effects to determine at what stage along the cognitive status continuum—without MCI vs. MCI—intervention is most effective. To do so, we will examine three-way interactions (MCI x training group x time) for the CAP, cognitive, and everyday function composites. When an interaction is significant, we will stratify analyses by MCI status and examine effect sizes. Effect sizes from pre- to post- training relative to controls will be compared for participants with/without MCI. An alpha of .05 will be used for these analyses.

Participants who score 26 or higher on the MoCA will be defined as no MCI (i.e., cognitively normal). Those participants who score a 20-25 on the MoCA will be defined as MCI if they score a 0.5 on the CDR and have performance at or 1 SD below their age, sex, and education norms on any of the following measures: Trails, Verbal Fluency, Digit Coding, Craft Story Recall, Multilingual Naming Test, or Benson Complex Figure. Those with MoCA scores 20-25 who score 0 on the CDR, but have performance at or 1SD below expected for age, sex, and education will be adjudicated prior to analyses. If an individual scores 20-25 on the MoCA, and 0.5 on the CDR, but has performance above expected on all of the aforementioned measures, their case will be adjudicated prior to analyses. The study physicians will adjudicate such cases prior to coding of MCI status for final analyses.

To quantify the effects of piano training further, in addition to examining composite outcomes as detailed above, we will calculate and report effect sizes for pre-to-post change of piano training relative to controls for each individual measure of CAP, cognition, and everyday function for the sample overall as well as stratified by MCI status and among those who were adherent only (80% or more of sessions completed).

Additional Analyses. To address exploratory aim 3, with identification of significant effects from the analyses for aim 1, we will examine behavioral mediators of interventions to determine mechanisms. We hypothesize that improved CAP will mediate cognitive gains. We hypothesize that cognitive gains will mediate functional gains. Formal mediation tests using a bootstrapping technique as outlined by Hayes¹²⁷ and Selig and Preacher¹²⁸ will be used to examine these hypotheses. The pre-to-post differences will be captured by a latent score¹²⁸, whereby the post-test score will serve as the outcome with pre-test score covaried. Results yield estimates and confidence intervals for the indirect and total effects. The procedure allows simultaneous estimation of all three pathways (M on Y; X on M; X on Y, where M=mediator (CAP score), Y=outcome (cognition), and X=predictor (group assignment)) as well as adjustment for covariates (e.g., depression). The use of bootstrapping will ensure that power is not reduced from the main effect analyses¹²⁹. An alpha of .05 will be used for these analyses.

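### The nonparametric check gives the Wilcoxon signed-rank test as its example, which tests change over time and not the difference between arms

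*Combined protocol and SAP*

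**What the plan says.** Section 9.6, under the paragraph on score distribution, sets a condition and a response. The condition is "In the event that distributional properties do not support parametric tests, we will compare the results from conventional parametric analyses with" a short list of alternatives. Item (a) of that list is "results from similar nonparametric testing (e.g., Wilcoxon signed ranks test"). Item (b) repeats the parametric analysis after transforming the non-normal variables. Item (c) checks illegal values and outliers against the raw data.

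The analysis being checked is described under Specific Aim 1 in the same section: "We will compare changes in performance for piano training relative to control across the two measurement points (baseline, immediate post-test"). The model is a repeated-measures mixed model "examining group as the between-subjects factor and time as the within-subjects factor", and the efficacy test is stated directly: "The group x time interaction will indicate whether the participants randomized to piano training change at differential rates". The significance threshold is "in our case a two-tailed p value of .05", with a Holm-Bonferroni adjustment across composites.

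Section 5.5 gives the design: "Participants with and without MCI will be randomized in a 1:1 ratio to either piano training or the active control condition of music listening instruction". The arms are independent, and no participant in one arm is matched to a participant in the other.

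Section 9.8 names ordinal logistic models within GEE, but only for self-efficacy and for the piano and listening skill measures. No other rank-based method is named for the CAP, cognition or everyday function outcomes.

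**The concern.** A robustness check is useful only if it addresses the same question as the result it checks. With two visits, the group x time test is a two-sample comparison of change scores, and its rank counterpart is a rank-sum test on change. The signed-rank test is a paired, or one-sample, test. In this design the only pairs are a person's baseline and post-test scores, so it asks whether change differs from zero, either pooled or within one arm.

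An analyst who follows the example literally would set a test of time beside a test of treatment. If the two disagree, the disagreement says nothing about distributional assumptions. If they agree, that is no reassurance. Running the test separately in each arm and comparing the two p-values does not help, because a significant result in one arm and not in the other is not a test of their difference.

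Shifts common to both arms can arise in several ways. One is built into the design: the schedule of evaluations in Section 6 assigns different verbal fluency forms to baseline and post-test. A between-arm comparison cancels any such common shift, but a signed-rank test does not.

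**Working it through.** The plan states no figure for this check, so there is none to reproduce. The working has three steps.

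**1. What each test addresses.** Let D_P and D_M be the mean change in the piano and music listening arms, with 99 per arm (Section 9.3; the overall analytic n in Table 14.3 is also 198) and a common SD of change, s.

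- Group x time: D_P - D_M, with SE = s x sqrt(1/99 + 1/99) = 2s/sqrt(198).
- Time, averaged over arms: (D_P + D_M)/2, with SE = s/sqrt(198).

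With equal arms and equal variances the two estimates are uncorrelated. A pooled signed-rank test is the rank version of the second. It responds to a treatment effect only through the average change, where it cannot be separated from change common to both arms.

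**2. The reported results.** If the time row of Table 14.2 is the average over arms, the interaction SE should be twice the time SE. If it were the change in one reference arm, the ratio would be sqrt(2). The ratio is 2 throughout, so the time row corresponds to the pooled within-person change that a pooled signed-rank test examines.

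| Outcome | Time: estimate / SE = z | p | Group x time: estimate / SE = z | p | 2 x time SE |
|---|---|---|---|---|---|
| ATTR | -2.77 / 0.68 = -4.07 | <.001 | 1.51 / 1.35 = 1.12 | .265 | 1.36 |
| CAP | 2.29 / 0.36 = 6.36 | <.001 | 0.465 / 0.71 = 0.65 | .515 | 0.72 |
| Verbal fluency | 0.41 / 0.48 = 0.85 | .393 | -0.29 / 0.96 = -0.30 | .763 | 0.96 |
| Cognition | -1.40 / 0.42 = -3.33 | .001 | 0.39 / 0.84 = 0.46 | .638 | 0.84 |
| Timed IADL | 0.14 / 0.79 = 0.18 | .863 | -1.53 / 1.58 = -0.97 | .327 | 1.58 |
| Test of Everyday Attention | -8.61 / 0.67 = -12.85 | <.001 | -0.40 / 1.34 = -0.30 | .765 | 1.34 |

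The p-values are as reported. Four of the six outcomes show a clear time effect and none shows a group x time effect. Lower ATTR scores are better, so ATTR and CAP improved, while cognition and the Test of Everyday Attention declined.

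**3. Simulation of change scores.** The settings were 99 per arm, normal change scores, two-sided alpha .05, 10,000 runs for the CAP-sized case and 5,000 for the others. For CAP, s = 0.36 x sqrt(198) = 5.07, so the change is 2.29/5.07 = 0.45 SD. The first four columns of results are the percentage of runs with p < .05.

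| True change (piano, control) | Signed-rank, piano | Signed-rank, control | Signed-rank, pooled | Rank-sum on change | One arm significant, the other not |
|---|---|---|---|---|---|
| Equal, CAP-sized (0.45 SD) | 99.3 | 99.1 | 100 | 5.2 | 1.6 |
| Equal, 0.2 SD | 49 | 48 | 78 | 4.8 | 49 |
| Equal, 0.1 SD | 17 | 16 | 29 | 5.1 | 28 |
| Opposite, +0.2 and -0.2 SD | 49 | 48 | 4.1 | 78 | 49 |

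In the first three rows there is no treatment effect. The rank-sum test holds its nominal 5%, and the signed-rank test rejects according to how large the common change is. In the last row the arms truly differ, and the pooled signed-rank test does not detect it. With heavier-tailed (Laplace) change scores and an equal change of 0.2 SD, the pooled signed-rank test rejects in 91% of runs and the rank-sum test in 5.5%.

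**The case against.** The case for leaving the text alone has four parts.

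- **It is only an example.** The test is introduced as an illustration of methods similar to the parametric ones. For Aim 1 the parametric method is group x time, so a between-arm rank test is within the wording. That is correct and lowers the weight. It does not remove the error, because the one test named for these outcomes does not match the analysis it is said to resemble.
- **The test has a proper use here.** Time is a factor in the model, and Section 14 interprets time effects. The signed-rank test is the right analogue for that term. This stands, but efficacy is not judged on that term.
- **The arm comparison is protected elsewhere.** Item (b) of the same list and the outlier analysis in Section 9.7 both keep the group x time test. This also stands: the gap is in one check, not in the plan's robustness checks as a whole.
- **The simulation shows what follows by definition.** That is fair. It shows the size of the mismatch and does not show that any conclusion was at risk.

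A reader might infer that the reported null result rests on the wrong test. The documents do not support this: the text and tables of Section 14 use the mixed model's group x time term and show no signed-rank result. A reader might also expect skewed Trails or Timed IADL times to trigger the problem through practice effects. No skewness is reported for either, Timed IADL shows no time effect (p = .863), and two of the four significant time effects are declines.

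**Conclusion.** The example in item (a) is a specification error, and a minor one. Used as named, the check can neither confirm nor contradict the treatment result, and a common change of either direction could make it significant. Table 14.2 shows that such changes occurred in four of six outcomes, with no group x time p below .265.

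The weight is small because the check is conditional on non-normality, sits beside the primary mixed model without replacing it, and is given only as an example. The reported null finding is not in question.

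The structural conclusion rests on the two-arm, two-visit design alone. The simulated rejection rates also assume 99 per arm, equal variances, and normal (or, in one case, Laplace) change scores. The CAP-sized case further assumes that the reported time SE equals s/sqrt(198). That gives an interaction SE of 0.72, against 0.71 reported.

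**What to change.** In item (a) of the score-distribution paragraph of Section 9.6, replace the signed-rank example with a between-arm rank method.

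- **Preferred:** a rank-based ANCOVA of the post-test score on arm, with baseline score, MCI stratum and the covariates used in the primary model (in Section 14: hearing, visual acuity and expectations). This keeps the check close to the analysis it is checking.
- **Alternative:** a rank-sum test on pre-to-post change stratified by MCI status (van Elteren), which matches the stratified randomization in Section 5.5. It is simpler but omits the covariates.

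If a rank test of the time effect is also wanted, the signed-rank test can stay, labelled as such.

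The cost is one phrase and one short analysis. The downside is that either option uses only participants with both visits, whereas the mixed model can include those with a missing post-test. Section 14 reports that 76% of randomized participants completed post-test, so the check should be labelled complete-case. The signed-rank test has the same limitation, so nothing is lost against the current text. Data collection ended in April 2021, so the change should be recorded as a dated clarification and not presented as prespecified.
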